9.3 Physical Examination and Vital Signs Data

Summary statistics for changes from baseline in vital signs will be provided for the Safety Sample. By-patient listings will be provided for physical examination.

Confidential - Proprietary Information

14

Potentially clinically relevant vital signs measurements identified in the open-label treatment phase for the Safety Sample will be listed and summarized. Criteria for identifying vital signs of potential clinical relevance are provided in Appendix 1.

In addition, the change from baseline in weight, BMI, and waist circumference, and potentially clinically relevant abnormalities in weight, will also be summarized.

9.4 12-Lead ECG

Summary statistics and incidence of potentially clinically relevant changes will be provided for ECG parameters.

For the analysis of QT and QTc, data from three consecutive complexes (representing three consecutive heart beats) will be measured to determine average values. The following QT corrections will be used for reporting purposes in the clinical study report:

- 1) QTcB is the length of the QT interval corrected for heart rate by the Bazett formula: QTcB=QT/(RR)^{0.5} and
- 2) QTcF is the length of the QT interval corrected for heart rate by the Fridericia formula: QTcF=QT/(RR)^{0 33}
- 3) QTcN is the length of the QT interval corrected for heart rate by the FDA Neuropharm Division formula: QTcN=QT/(RR)^{0 37}

Potentially clinically relevant changes in the 12-lead ECG identified in the open-label treatment phase for the Safety Sample will be listed and summarized. Criteria for identifying ECG measurements of potential clinical relevance are provided in Appendix 3.

Categorical changes in ECG parameters during the open-label treatment phase will be summarized based on the following criteria:

[figure not shown]
Categorical Change Criteria in QT/QTc Parameters				
Classification	Category	Criteria		
QT	New Onset (> 450 Msec)	New onset (>450 msec) in QT means a subject who		
		attains a value > 450 msec during treatment period		
		but not at baseline.		
QTc * New Onset (≥ 450 Msec New onse		New onset (≥ 450 Msec for men and (≥ 470 Msec		
	for men and \geq 470 Msec	for women) in QTc means a subject who attains a		
	for women)	value ≥ 450 Msec for men or ≥ 470 Msec for		
		women during treatment period but not at baseline.		
	New Onset (≥ 450 Msec	New onset (≥ 450 Msec for men and ≥ 470 Msec for		
	for men and \geq 470 Msec	women) and		
	for women)	> 10% increase in QTc means a subject who attains		
	And > 10% Increase	a value ≥ 450 Msec for men or ≥ 470 Msec for		

Confidential - Proprietary Information

15

Categorical Change Criteria in QT/QTc Parameters			
Classification Category Criteria		Criteria	
		women, and > 10% increase during treatment period but not at baseline	
	New Onset (> 500 Msec)	New onset (> 500 msec) in QTc means a subject who attains a value > 500 msec during treatment period but not at baseline.	
	Increase 30 - 60 Msec	Increase from baseline value > 30 and ≤ 60 msec in OTc	
	Increase > 60 Msec Increase from baseline value > 60 msec in QTc		

^{*} QTc categorical change criteria apply to QTcB, QTcF and QTcN.

9.6 Concomitant Medications

Number and proportion of patients taking concomitant medications prior to the open-label treatment phase, during the open-label treatment phase, and after study therapy are tabulated by drug classification using the WHO drug dictionary.

[figure not shown]
Confidential - Proprietary Information

16

9.7 Extent of Exposure

[figure not shown]
The start date of the open-label study therapy - brexpiprazole - will be the first day of dosing during the open-label treatment phase. The number and percentage of patients who receive study medication during the open-label treatment phase, will be presented by week. Each dosing week will be based on the actual week; i.e., Day 1-7 in Week 1, Day 8-14 in Week 2, etc. This summary will be performed on the Safety Sample.

The mean daily dosage will be summarized by week using descriptive statistics. The mean daily dosage per patient per week will be determined for each week of the study. This will be calculated by dividing the sum of individual total doses by the number of days in the week interval. The summary will contain the number of patients receiving study medication during the open-label treatment phase, and the mean and range of the mean daily dose for each week.

Confidential - Proprietary Information

17

[figure not shown]

Confidential - Proprietary Information

10 July 2019

Until the information herein is released by Otsuka to the public domain, the contents of this document are Otsuka confidential information and should not be duplicated or re-distributed without prior written consent of Otsuka.

18

Confidential - Proprietary Information

19

10 July 2019

Until the information herein is released by Otsuka to the public domain, the contents of this document are Otsuka confidential information and should not be duplicated or re-distributed without prior written consent of Otsuka.

Confidential - Proprietary Information

20

11 Potential Clinical Relevance Criteria from Protocol

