#### 3.3 Trial Population

# 3.3.1 Number of Subjects and Description of Population

It is estimated that approximately 384 rollover subjects may be enrolled into Trial 331-201-00083 to achieve a target completion of approximately 175 subjects at 6 months at approximately 90 trial sites in North America and the rest of world (ROW). Men and women 18 to 65 years of age with a Diagnostic and Statistical Manual of Mental Disorders, Fifth Edition (DSM-5) diagnosis of bipolar I disorder will be enrolled in the trial and will include rollover subjects from the double-blind, phase 3 efficacy trials (ie, Trials 331-201-00080 or 331-201-00081). In the event the sponsor determines that the enrollment rate of rollover subjects will not be sufficient to meet the target completion of approximately 175 subjects at 6 months, de novo subjects may be enrolled at select sites. The enrollment of de novo subjects at any site will not be permitted until initiation and notification by the sponsor.

Diagnosis will be confirmed by the Mini International Neuropsychiatric Interview (MINI) and a history of at least 1 previous manic episode with or without mixed features and manic symptoms of sufficient severity to require one of the following interventions: hospitalization or treatment with a mood stabilizer, or treatment with an

Confidential - Proprietary Information

26

<sup>bOption to titrate to 2 to 4 mg (ie, 2 mg, 3 mg, or 4 mg) based on clinical response and tolerability; changes must occur in 1 mg/day increments. Increases up to 4 mg/day may occur no earlier than Day 7.

antipsychotic agent. Eligible subjects must not currently have severity of bipolar symptoms that, in the opinion of the investigator, would require hospitalization. Approximately 60% of subjects will be enrolled from North America and 40% of subjects will be enrolled from the rest of world (ROW).

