3.2 Trial Treatments

Rollover Subjects

- The first dose of open-label brexpiprazole (OPC-34712) will be taken one day after the last dose of double-blind IMP is taken in Trials 331-201-00080 or 331-201-00081 so that treatment continues without interruption. It is anticipated that the last dose of the double-blind, phase 3 efficacy trial will be taken the day of the Day 21 (Week 3) visit of Trial 331-201-00080 or 331-201-00081 (ie, the day of the screening/baseline visit for the open-label trial).
- All subjects will start on 2 mg/day of brexpiprazole (OPC- 34712) regardless of treatment assignment in the double-blind trial.

All subjects will receive a starting dose of 2 mg/day of brexpiprazole from Days 1 to 3, followed by titration to 3 mg/day brexpiprazole on Day 4. Subjects may be titrated (or retitrated) to a higher dose of brexpiprazole, up to a maximum of 4 mg/day, based on treatment response and at the investigator's discretion anytime at Day 7 or thereafter. Subjects who are unable to tolerate their current dose can be titrated down at any time to a minimum of 2 mg/day. Dose adjustments must be made in increments of 1 mg/day. Subjects who are unable to tolerate 2 mg/day brexpiprazole will be discontinued from the trial.

The dosing strategy is summarized in Table 3.2.2.1-1. Subjects must return to the clinic for unscheduled visits if dose adjustments for brexpiprazole are required between scheduled visits. Dose adjustments must ultimately be made based upon the clinical judgment of the investigator as it relates to tolerability and therapeutic response. All doses of brexpiprazole should be taken orally once daily and can be administered without regard to meals. Subjects are to take IMP at approximately the same time each day.

Table 3.2.2.1-1 Dosing Schedule - Open-label Treatment Phase			
	Trial Visit		
IMP	Days 1-3	Day 4 ^a	Day 7-Week 26
Brexpiprazole (OPC-34712)	2 mg/day	3 mg/day	2-4 mg/day ^b

^aDown titration can occur at any time due to tolerability after Day 4. The minimum dose allowed is 2 mg/day.

Confidential - Proprietary Information

7

^bOption to titrate to 2 to 4 mg (ie, 2 mg, 3 mg, or 4 mg) based on clinical response and tolerability; changes must occur in 1 mg/day increments. Increases up to 4 mg/day may occur no earlier than Day 7.

4 Sample Size and Power Justification

[figure not shown]

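### SAP 9.7 divides a partly dosed final week by seven days, so the weekly exposure table would print a dose lower than the one taken

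*SAP*

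**What the plan says.** SAP section 9.7 (Extent of Exposure) starts the clock on the first day of open-label dosing and then fixes the weeks: "Each dosing week will be based on the actual week; i.e., Day 1-7 in Week 1, Day 8-14 in Week 2, etc". The calculation covers every patient and every week: "The mean daily dosage per patient per week will be determined for each week of the study". The value is found by "dividing the sum of individual total doses by the number of days in the week interval". The summary then shows, beside the number of patients receiving drug, "the mean and range of the mean daily dose for each week".

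The visible text has no rule for a block cut short by the last dose. It does not say that the divisor means days on treatment, and it does not say where dosing after Day 182 goes.

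Other relevant places:
- The dosing table in SAP section 3.2 sets the floor: "The minimum dose allowed is 2 mg/day".
- Protocol Table 3.7-1 gives the Week 26 visit a window of ±2 days.
- Protocol section 3.10 defines a completer by attendance at the Week 26 visit, not by a last-dose day.
- Protocol section 3.3.1 expects about 384 enrolled and about 175 completing.

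**The concern.** This is a flexible-dose safety trial, and the weekly dose table tells the reader what dose the adverse event data describe. If days after the last dose enter as zeros, the value for a patient's final block mixes the dose taken with the day on which treatment stopped.

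The range suffers most, because one patient sets the minimum. A low minimum ought to signal missed doses. Here it would mostly signal that someone stopped that week, and it would sit below a dose the plan does not allow. The last rows, which describe exposure at six months, could also show a fall in dose that did not happen.

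**Working it through.** The plan gives no numerical exposure figure to reproduce, so the check applies the rule of section 9.7 directly.

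**1. One patient, final block.** Rule: value = (sum of daily doses in the block) / 7. With constant dose D and last dose on day d of the block, this is D × d / 7.

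| Last dose on block day | 1 | 2 | 3 | 4 | 5 | 6 | 7 |
|---|---|---|---|---|---|---|---|
| 2 mg/day prints | 0.29 | 0.57 | 0.86 | 1.14 | 1.43 | 1.71 | 2.00 |
| 3 mg/day prints | 0.43 | 0.86 | 1.29 | 1.71 | 2.14 | 2.57 | 3.00 |
| 4 mg/day prints | 0.57 | 1.14 | 1.71 | 2.29 | 2.86 | 3.43 | 4.00 |

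At 3 mg/day, a stop on days 1 to 4 prints below 2 mg/day. At 4 mg/day, days 1 to 3 do. Only day 7 prints the dose taken.

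**2. Weekly means.** Expected early stops are 384 − 175 = 209, or 209 / 26 = 8.04 per week if spread evenly. With a uniform stop day the average fraction printed is (1 + 2 + … + 7) / 49 = 4/7, so a stopper at 3 mg/day averages 1.71. With n patients on treatment the mean is [3 × (n − 8.04) + 1.71 × 8.04] / n:
- n = 384: 2.97
- n = 280: 2.96
- n = 175: 2.94

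**3. Weekly minimum.** If everyone takes 3 mg/day and k patients stop at uniform days in a week, the chance that the minimum prints below 2 mg/day is 1 − (3/7)^k. That is 57% for k = 1 and 99.9% for k = 8.

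**4. Simulation of both.** 400 trials of 384 subjects, exponential stopping times with rate −ln(175/384)/182 = 0.0043 per day, everyone on 3 mg/day after titration, full adherence. In Weeks 2–25 the mean prints 2.96 against 3.00. The weekly minimum averages 0.55 to 0.79 mg/day, depending on the week, and falls below 2 mg/day in about 99% of week rows.

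**5. Completers.** Week 26 nominally ends on Day 26 × 7 = 182, so the visit may fall on Days 180 to 184. At 3 mg/day, with the last dose on the visit day:

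| Last dose | Week 26 prints | Week 27, if a row is printed |
|---|---|---|
| Day 180 | 2.14 | – |
| Day 181 | 2.57 | – |
| Day 182 | 3.00 | – |
| Day 183 | 3.00 | 0.43 |
| Day 184 | 3.00 | 0.86 |

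With last-dose days uniform over this window, the completer mean for Week 26 is (2.14 + 2.57 + 3 × 3.00) / 5 = 2.74. Including patients who drop out during Week 26, the simulation gives 2.71. If every completer stops on Day 182, it gives 2.96 and no Week 27.

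**The case against.** The strongest reply is that the whole of the relevant text cannot be seen. Parts of section 9.7 and most of section 10 (Conventions) are not visible. The SAP does write end-of-treatment rules elsewhere: section 6.2 uses the last recorded drug end date for patients lost to follow-up when computing compliance. A partial-week convention may therefore exist. This stands as a limit on certainty. If there is such a rule, section 9.7 should cite it.

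A programmer might also take the divisor to mean treated days in the interval. That is possible, but the wording attaches the days to the interval just defined as seven days, and the two readings produce different tables.

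Three stronger conclusions are tempting and go too far:
- **That the range would carry no information.** The maximum and the patient count are unaffected, and a genuine minimum could itself be 2 mg/day or lower. Protocol section 3.12 only asks sites to consider discontinuation when compliance is below 80%. The 3.00 comparator reflects the assumption of uniform dose and perfect adherence.
- **That one discontinuation puts the minimum below the floor.** At 3 mg/day a single stop does so 57% of the time. Near-certainty needs several stops per week, and the documents give no dropout timing.
- **That Week 26 is understated for most completers and a Week 27 row will appear.** No passage ties the last dose to a day within the visit window, and none says rows continue past Week 26.

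**Conclusion.** The point holds on the plain reading of section 9.7. Any block in which the last dose falls on days 1 to 6 prints less than the dose taken. At 3 mg/day the printed values are 0.43 to 2.57.

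Its size is modest. Under the stated assumptions, means in Weeks 2–25 move by about 1%. The visible damage is to the weekly minimum, which would usually be a stopping artefact below 2 mg/day. The last rows may also be affected: Week 26 lies between about 2.71 and 2.96 across the two last-dose assumptions tried, with a possible Week 27 row at 0.43 to 0.86.

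The table is descriptive, and no adverse event incidence, denominator or test depends on it. A reader might infer that the trial's dosing results would be broadly wrong or would show widespread underdosing; the figures do not support that. The change is worth making because the stated rule gives a misleading printed value and is easy to correct.

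**What to change.** In SAP section 9.7, define the divisor as the number of days in the block that fall between the patient's first and last open-label dose dates, inclusive. Missed days during treatment still count as zero; days after the last dose do not.

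Add that dosing after Day 182 is included in Week 26 with the divisor extended accordingly. A completer on 3 mg/day to Day 184 would then have 27 mg over the 9 days from Day 176, which is 3.00 mg/day. If a partial-week convention already exists elsewhere in the SAP, cite it in section 9.7 instead.

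The cost is one or two sentences and a small change to the table program. It needs no new data, because dose dates are already required for this summary.

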Appendix 1 Criteria for Identifying Vital Signs of Potential Clinical Relevance

Variable	Criterion Value ^a	Change Relative to Baseline ^a	
Heart Rate ^b	> 120 bpm < 50 bpm	≥ 15 bpm increase ≥ 15 bpm decrease	
Systolic Blood Pressure ^b	> 180 mmHg < 90 mmHg	≥ 20 mmHg increase ≥ 20 mmHg decrease	
Diastolic Blood Pressure ^b	> 105 mmHg < 50 mmHg	≥ 15 mmHg increase ≥ 15 mmHg decrease	
Orthostatic Hypotension	≥ 20 mmHg decrease in systolic blood pressure and a ≥ 25 bpm increase in heart rate from supine to sitting/standing	Not Applicable (baseline status not considered)	
Weight	-	≥ 7% increase ≥ 7% decrease	

^a In order to be identified as potentially clinically relevant, an on-treatment value must meet the "Criterion Value" and also represent a change from the subject's baseline value of at least the magnitude shown in the "Change Relative to Baseline" column.

^b As defined in "Supplementary Suggestions for Preparing an Integrated Summary of Safety Information in an Original NDA Submission and for Organizing Information in Periodic Safety Updates," FDA Division of Neuropharmacological Drug Products draft (2/27/87).

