15.	Subjects with IDDM (ie, any subjects using insulin) are excluded. Subjects with non-IDDM may be eligible for the trial if their condition is stable as determined by satisfying ALL of the following criteria:  • HbA1c < 7.0%, AND
	• Screening glucose must be ≤ 125 mg/dL (fasting) or < 200 mg/dL (nonfasting). If the nonfasting screening glucose is ≥ 200 mg/dL, subjects must be retested in a fasted state and the retested value must be ≤ 125 mg/dL, AND
	• Subject has been maintained on a stable regimen of oral anti-diabetic medication(s) for at least 28 days prior to screening or diabetes has been well-controlled by diet for at least 28 days prior to screening, AND
	
 
Subject has not had any hospitalizations within the 12 months prior to screening due to diabetes or complications related to diabetes, AND
 
Subject's diabetes is not newly diagnosed during screening for the trial.
 

16.	Subjects with uncontrolled hypertension (DBP > 95 mmHg in any position) or symptomatic hypotension, or orthostatic hypotension which is defined as a decrease of ≥ 30 mmHg in SBP and/or a decrease of ≥ 20 mmHg in DBP after at least 3 minutes standing compared to the previous supine blood pressure, OR development of symptoms.
	NOTE: Blood pressure measurements may be repeated once to ensure reproducibility of the exclusionary result(s) before excluding a subject based on the criteria noted above.
17.	Subjects with epilepsy or a history of seizures, except for a single seizure episode; for instance childhood febrile, post traumatic, or alcohol withdrawal seizure.

Physical and Laboratory Results	

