<sup>aFor rollover subjects, screening for Trial 331-201-00083 occurs simultaneously with baseline which will be at the same day as the Day 21 (Week 3) visit of Trial 331-201-00080 or Trial 331-201-00081. Separate screening and baseline visits are required for de novo subjects to allow for completion of eligibility assessments and washout of prohibited concomitant medications, if applicable. The enrollment of de novo subjects at any site will not be permitted until initiation and notification by the sponsor.

Confidential - Proprietary Information

36

<sup>bIf a subject discontinues early before Week 26, procedures noted for Week 26 must be completed at the ET visit. Attempts should be made to complete ALL evaluations, particularly efficacy assessments, for the Week 26/ET visit prior to the administration of any new psychotropic medications. However, if the subject receives a new antipsychotic prior to ET procedures, no efficacy assessments should be done. Any prohibited medications started before the end of the trial assessments should be documented as a protocol deviation in the source notes.

<sup>gBaseline assessment will be performed at baseline of Phase B for de novo subjects who enter Phase B directly after screening, but will be obtained from the Conversion Week 4 visit of Phase A for subjects who participate in Phase A.

Vital signs include body weight, body temperature, systolic blood pressure (SBP), diastolic blood pressure (DBP), and heart rate. Blood pressure and heart rate will be measured in the following order: supine and standing after the subject has been in each position for at least 3 minutes. Vital signs scheduled for the same visit as blood samples are to be completed before blood is drawn.

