## 3.7.3.3.2 Measurement of Vital Signs

The measurement of vital signs will include body weight, body temperature, systolic blood pressure (SBP), diastolic blood pressure (DBP), and heart rate. The following guidelines will aid in the standardization of body weight measurements:

- The same scale should be used to weigh a given subject each time, if possible.
- Scales should be calibrated and reliable; scales should be at zero just prior to each subject's weigh-in session.
- A subject should void prior to being weighed and be minimally clothed (ie, no shoes or heavy overgarments).
- Weight should be recorded before a subject's meal and at approximately the same time at each visit.

Blood pressure and heart rate measurements will be made in the supine and standing positions after the subject has been in each position for at least 3 minutes. The supine measurements will be performed first followed by standing.

Subjects with uncontrolled hypertension (screening DBP > 95 mmHg in any position) or symptomatic hypotension are excluded from the trial as are subjects with orthostatic hypotension defined as a decrease of  $\geq$  30 mmHg in SBP and/or a decrease of  $\geq$  20 mmHg in DBP after at least 3 minutes standing compared to the previous supine blood pressure OR development of symptoms (see Table 3.4.3-1). In addition, subjects

should be excluded if they have any other vital sign measurement at screening that, in the investigator's judgment, is medically significant in that it would impact the safety of the subject or the interpretation of the trial results. However, any abnormal screening vital sign result(s) considered to be clinically significant should be repeated to confirm the finding(s) before excluding the subject from the trial. Appendix 6 is included to assist investigators in their assessments of results that may be potentially medically significant, depending on the subject's medical history and clinical presentation.

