#### 4.2 Other Restrictions

The subject's best medical interests should guide the investigator in the management of conditions that are pre-existing or that develop during the trial (intercurrent illness or AEs). The investigator should examine the acceptability of all concomitant medications not explicitly prohibited. In order to ensure that appropriate concomitant therapy is administered, it is essential that subjects be instructed not to take any medications (either self-administered non-prescription drugs or prescription therapy prescribed by another physician) without prior consultation with the investigator. In particular, the investigator should caution the subject about concomitant use of the following during the trial:

- Non-steroidal anti-inflammatory drugs, aspirin, or other drugs that interfere with coagulation since the combined use of psychotropic drugs that interfere with serotonin reuptake and these agents has been associated with an increased risk of upper gastrointestinal bleeding.
- Triptans (eg, sumatriptan, naratriptan, almotriptan, frovatriptan, rizatriptan, eletriptan, and zolmitriptan), linezolid, and methylene blue since there have been rare post-marketing reports of serotonin syndrome or serotonin syndrome-like reactions (eg, mental status changes, hyperreflexia, autonomic effects, lack of coordination, and

diarrhea) following the concomitant use of SSRIs or serotonin-norepinephrine reuptake inhibitors and these drugs.

Anticholinergics are permitted for the treatment of EPS up to a maximum of 4 mg/day benztropine or its equivalent and propranolol is permitted for akathisia or tremor up to a maximum of 20 mg 3 times daily (total of 60 mg/day). Sites should only utilize medications that are approved for these indications in their respective countries.

All trial personnel should be familiar with the content of the IB for brexpiprazole in order to manage the subject's condition adequately and select appropriate concomitant medications, if needed.

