# Appendix 6 Criteria for Identifying Vital Signs of Potential Clinical Relevance

Variable	able Criterion Value a			
Heart rate b	> 120 bpm	≥ 15 bpm increase		
Heart rate	< 50 bpm	≥ 15 bpm decrease		
b	> 180 mmHg	≥ 20 mmHg increase		
Systolic blood pressure	< 90 mmHg	≥ 20 mmHg decrease		
b	> 105 mmHg	≥ 15 mmHg increase		
Diastolic blood pressure	< 50 mmHg	≥ 15 mmHg decrease		
	≥ 20 mmHg decrease in systolic blood	Not applicable		
Orthostatic hypotension	pressure and a ≥ 25 bpm increase in heart rate from supine to sitting/standing	(baseline status not considered)		
Weight		≥ 7% increase		
Weight	泰	≥ 7% decrease		

<sup>3In order to be identified as potentially clinically relevant, an on-treatment value must meet the "Criterion Value" and also represent a change from the subject's baseline value of at least the magnitude shown in the "Change Relative to Baseline" column.

<sup>bAs defined in "Supplementary Suggestions for Preparing an Integrated Summary of Safety Information in an Original New Drug Application Submission and for Organizing Information in Periodic Safety Updates," FDA Division of Neuropharmacological Drug Products draft (2/27/87).

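### The on-treatment orthostatic hypotension flag requires a heart-rate rise of at least 25 bpm and has no diastolic limb, so some measured falls that meet the protocol's own definition are not counted

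*SAP*

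**What the plan says.** SAP 9.3 lists and summarises potentially clinically relevant vital signs in the open-label phase for the Safety Sample, using the criteria in SAP Appendix 1, headed "Criteria for Identifying Vital Signs of Potential Clinical Relevance". The orthostatic hypotension row there reads "≥ 20 mmHg decrease in systolic blood pressure and a ≥ 25 bpm increase in heart rate from supine to sitting/standing", and its change-from-baseline column says that baseline status is not considered. Protocol Appendix 6 carries the same rule ("pressure and a ≥ 25 bpm increase in heart rate from supine to sitting/standing"), so the SAP follows the protocol.

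Elsewhere the protocol defines the term differently. Exclusion 16 in Table 3.4.3-1 refers to "orthostatic hypotension which is defined as a decrease of ≥ 30 mmHg in SBP and/or a decrease of ≥ 20 mmHg in DBP", measured after at least 3 minutes standing against the preceding supine reading, or the development of symptoms. Section 3.7.3.3.2 repeats those thresholds and states that such subjects are excluded. Neither place mentions heart rate.

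On positions, the footnotes to Table 3.7-1 say: "Blood pressure and heart rate will be measured in the following order: supine and standing". No sitting reading is planned. Vital signs are scheduled at baseline and at Weeks 1, 2, 4, 8, 12, 18 and 26/ET.

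**The concern.** One term has two definitions, and they differ in kind. The on-treatment flag adds a second variable that must move at the same time, and it drops the diastolic and symptom limbs. The readable text does not explain why. Footnote b of the appendix, which cites an FDA draft as the source of the criteria, is attached to the heart rate, systolic and diastolic rows and not to the orthostatic row.

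Safety and tolerability are the trial's only objective, and the flag feeds a reported summary. A reader of that summary would take a low orthostatic count to mean that few subjects had a marked postural fall. Under the current rule it means only that few had a systolic fall together with a large rise in heart rate. Mean changes from baseline, also planned in SAP 9.3, do not count postural falls in individuals.

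**Working it through.** No sample size, power or event figure is involved. The check compares the two rules on supine-to-standing changes.

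**Notation.** S = systolic fall (mmHg), D = diastolic fall (mmHg), H = heart-rate rise (bpm).

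- Protocol definition, measured part (exclusion 16; 3.7.3.3.2): S ≥ 30 or D ≥ 20.
- On-treatment flag (SAP Appendix 1; protocol Appendix 6): S ≥ 20 and H ≥ 25.

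**Step 1: where the rules disagree.**

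- Definition met, flag not raised: (S ≥ 30 and H < 25), or D ≥ 20 with (S < 20 or H < 25).
- Flag raised, definition not met: S from 20 to below 30, D < 20, H ≥ 25, no symptoms.

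| S / D / H | Protocol definition | On-treatment flag |
|---|---|---|
| 40 / 10 / 10 | yes | no |
| 60 / 30 / 5 | yes | no |
| 40 / 25 / 24 | yes | no |
| 10 / 25 / 30 | yes | no |
| 19 / 30 / 40 | yes | no |
| 30 / 20 / 25 | yes | yes |
| 25 / 10 / 30 | no | yes |

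Rows four and five show that a diastolic fall with S below 20 is never flagged as orthostatic hypotension, whatever the heart rate.

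**Step 2: whether the other rows recover the missed cases.** The low-systolic row needs a value below 90 mmHg and a decrease of at least 20 from baseline. The low-diastolic row needs a value below 50 mmHg and a decrease of at least 15. If these rows are applied to standing values:

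- a 30 mmHg systolic fall ends below 90 only if supine systolic pressure is below 90 + 30 = 120;
- a 20 mmHg diastolic fall ends below 50 only if supine diastolic pressure is below 50 + 20 = 70.

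The change-from-baseline condition must hold as well. A case caught this way is counted as low pressure and not as orthostatic hypotension.

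**Step 3: a worked case.** Supine 140/85, heart rate 72; standing 100/62, heart rate 88. Then S = 140 − 100 = 40, D = 85 − 62 = 23, H = 88 − 72 = 16. Both blood-pressure limbs of the protocol definition are met. The flag is not raised, because 16 < 25. The standing values are not below 90 or below 50, and heart rate is between 50 and 120, so no other blood-pressure or heart-rate row applies, whatever the baseline.

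**Step 4: size.** Among measurements with S ≥ 30, the share flagged is P(H ≥ 25). Neither document gives a mean or SD for H. For illustration only, with H normal and SD 10, the share is 1 − Φ((25 − mean)/10): 7% for an assumed mean of 10, 16% for 15 and 31% for 20. These are per measurement. If such a fall recurred at all seven post-baseline visits and visits were independent (two further assumptions), the chance of at least one flag is 1 − (1 − p)^7, or about 38%, 70% and 92%. A range from 7% to 92% driven wholly by assumption does not give a size.

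**The case against.** **Entry limits and on-treatment flags differ by design.** Diastolic pressure excludes above 95 mmHg but is flagged above 105 with a rise of at least 15. AST and ALT exclude above 2 × ULN but are flagged at 3 × ULN or more. A difference is therefore not a contradiction in itself, and the rule was prospectively defined. This stands as far as it goes. In those examples, however, the same quantity is judged at another threshold. Here the heart-rate condition is new and the diastolic limb is gone.

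**Other routes exist.** Symptomatic events can enter the adverse event tables, and low pressures have their own rows. Parts of the SAP are redacted and its table list is not shown, so a further orthostatic summary cannot be ruled out. This stands, and it limits the point to measured falls, mainly those without symptoms, and to the readable text.

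**Stronger readings that a reader might infer, and that the documents do not support:**

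- *That the SAP departs from the protocol.* It does not; the rule is in both.
- *That the flag is stricter throughout.* Its systolic limit is lower, 20 against 30 mmHg.
- *That missed subjects would have been barred at entry.* Exclusion 16 is listed for de novo subjects, and the SAP says that none were enrolled. Section 3.7.3.3.2 states the exclusion without that limit but refers back to the same table. The safe statement is that these falls meet the protocol's own definition.
- *That propranolol users are the least likely to be detected.* Protocol 4.2 says only that "propranolol is permitted for akathisia or tremor up to a maximum of 20 mg 3 times daily". Its effect on postural heart rate and how many subjects took it are not given.
- *That the receptor profile in the protocol introduction predicts postural falls.* That section lists affinities and says nothing about blood pressure.

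**Conclusion.** The concern holds in limited form. SAP Appendix 1 and protocol Appendix 6 do not flag, as orthostatic hypotension, falls that meet the protocol's own definition when heart rate rises by less than 25 bpm. They never so flag a diastolic fall with a systolic fall below 20 mmHg. The low-pressure rows catch only some of these. In the other direction, the current row counts systolic falls of 20 to 29 mmHg with a rise of at least 25 bpm that the protocol definition can leave out.

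The gap follows from the wording of the two rules and needs no assumption. Its size cannot be computed from the documents, so a claim that the orthostatic count will read near zero is not supported. No view is taken on which definition is clinically right; the point is that two definitions are in use and only one is analysed in the readable text. This is a cheap improvement and does not affect the primary adverse event analysis.

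**What to change.** Reconcile the two definitions for analysis:

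1. Keep the current row in SAP Appendix 1, labelled as systolic fall with heart-rate rise.
2. Add a supplementary row to Appendix 1 and to the SAP 9.3 summary: supine-to-standing fall of at least 30 mmHg systolic and/or at least 20 mmHg diastolic after at least 3 minutes standing. Label it as the measured part of the protocol definition, since symptoms are not part of it.
3. Report any on-treatment occurrence by parent-study treatment group and overall, and split it by whether the fall was present at open-label baseline. Do not restrict to new onset. Rollover baseline is the Day 21 visit of the double-blind trial, on double-blind IMP, so a new-onset count would hide falls that began on brexpiprazole in the parent trial.
4. Replace *sitting/standing* with *standing*, because no sitting values are planned.
5. Optionally, show the new row by propranolol use.

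The supine and standing readings are already scheduled at baseline and every treatment visit, so no new data are needed. The cost is one more table row and a higher reported frequency.
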